4.2. Rationale

Although well tolerated by most patients, about 30% of patients undergoing RT develop a Grade 2 or worse early adverse skin reaction (EASR). One study in Taiwan showed 23% of patients

Version: 00

techniques, a significant number of patients experience skin toxicity⁴.

Effective Date: 03-01-2018

undergoing chest wall or whole breast irradiation developed moist desquamation based on the RTOG scale⁵. This scale described grade 2 skin toxicity as tender or bright erythema, patchy moist desquamation / moderate erythema; Grade 3 skin toxicity was described as confluent moist desquamation other than skin fold, pitting edema. Both grade 2 and 3 skin toxicities were recorded in the assessment of patients in the Taiwanese study. Another study comparing breast IMRT to conventional tangent fields showed a decrease in moist desquamation, as defined by the NCI CTC version 2, from 48% to 31% of patients, suggesting that even with advanced treatment

For this study, we will classify grade 2 or 3 skin toxicity (per the RTOG scale) as an EASR. Beyond the discomfort patients may experience, EASRs may result in poor patient outcomes. Severe EASRs can require a "treatment break" which, in some cancers, may result in incomplete tumor control and greater chance of local recurrence and lower survival rates. In addition to the potential impact on cancer outcomes, EASRs may affect patients' self-esteem due to the appearance of their skin and recovery time after treatment. Standard skin regimens often include routine application of creams or lotions in an effort to combat the dryness, prevent interruption of the skin's natural barrier (e.g., cracking or flaking), and reduce the appearance of inflammation. Patients often begin using these creams/lotions at the start of RT. Providing patients with a product that moisturizes and reduces the appearance of inflammation may improve patients' satisfaction with their appearance as they progress through RT treatment.

KeraNetics has determined that this study is a non-significant risk study under 21 CFR 812.3(m). This device is not intended as an implant. It is not for use supporting or sustaining human life. It is not for a use of substantial importance in diagnosing, curing, mitigating, or treating disease or otherwise preventing impairment of human health, and it does not otherwise present a serious risk to health, safety, or welfare of a subject. Furthermore, KeraStat Cream is classified as a wound dressing; wound dressings are classified as nonsignificant risk devices in FDA's "Information Sheet Guidance for IRBs, Clinical Investigators, and Sponsors: Significant Risk and Nonsignificant Risk Medical Device Studies" published January 2006.

5. TRIAL OBJECTIVES AND PURPOSE

5.1. Objectives

The primary objectives of the proposed research are to evaluate the feasibility of the use of KeraStat Cream and collect data to inform a larger future trial.

The secondary objectives are to assess the safety and tolerability of KeraStat Cream in subjects at risk of radiation dermatitis, to assess the effectiveness of KeraStat Cream and how that compares to the current standard of care, and to estimate the amount of KeraStat Cream used per patient and coverage on skin.

Version: 00

Effective Date:

03-01-2018

6. INVESTIGATIONAL PLAN

6.1. Overall Study Design

This is a single site, between subject, open-label comparison pilot study to assess the feasibility and effectiveness of KeraStat Cream in managing RT skin toxicity. The length of study participation for a subject is 8-12 weeks depending on when a subject returns for her final follow-up evaluation. The Study Design Schematic is shown below in Figure 1 with the Acceptable Study Windows in Table 2.

Sufficient subjects will be screened such that 24 total subjects will complete the study. Patient compliance is expected to be good, so a target recruitment of 26 subjects is desired.

Once a RT patient is determined to be a candidate for inclusion in this study, they may be approached for consent to participate. A total of 26 breast cancer patients scheduled to receive RT will be recruited and consented.

RT will begin 4 to 10 weeks after surgery; the targeted volume will be the ipsilateral breast with or without regional lymph nodes. Once the patient has consented to participate in the study, their baseline pre-RT assessments can be completed during the radiation treatment-planning process.

Patients are generally treated with RT Monday through Friday, with weekends and holidays off, for approximately 4 to 6 weeks. Patients will be provided with KeraStat Skin Cream for application as often as needed but at least twice daily, morning and evening.

During the course of treatment, the patient sees the radiation oncologist weekly in clinic to review the patient's treatment course, monitor the skin's appearance after application of KeraStat Skin Cream or standard of care, and answer questions. Breaks in the treatment schedule should be avoided whenever possible, but breaks necessitated by RT skin toxicity or for other reasons will be recorded. The radiation oncologist will see each patient in follow-up 4-8 weeks after completing RT to assess the patient for RT-induced skin and other toxicities that may have occurred.

Version: 00

Effective Date: 03-01-2018

Figure 1: Study Design Schematic

Table 2: Acceptable Study Windows

Visit	Day Visit	Acceptable Visit Window
Screening (Visit 1)	Day 1	None
Baseline (Visit 1)	Day 1	None
First evaluation (Visit 2)	RT Day 8	±2 days
Second evaluation (Visit 3)	RT Day 15	±2 days
Third evaluation (Visit 4)	RT Day 22	±2 days
Fourth evaluation (Visit 5)	RT Day 29	±2 days
Fifth evaluation (Visit 6)	RT Day 36	±2 days
Final evaluation (Visit 7)	Post RT Day 30	±14 days

6.2. Detailed Study Design

6.2.1. Identification of Subjects and Consent

Study personnel will identify potential participants during radiation therapy treatment planning, explain the study, and seek to obtain subject consent. Individuals who express an interest will review and sign an informed consent form with study staff.

6.3. Number of Subjects

Twenty-six subjects are anticipated to be required for screening and enrollment in order to achieve a total of 24 patients participating in this study. Subjects will be randomized to receive either standard of care or KeraStat Cream.

Subjects at screening will be given a sequential subject number starting with 1001, 1002, etc. Subject initials will be collected, but not used as an identifier. The subject number will be used to identify the subject and all study materials associated with each subject.

Version: 00

Effective Date:

03-01-2018

6.4. Treatment Assignment

All subjects will be randomized to receive one of two test agents: KeraStat Cream or standard of care (physician-directed care).

6.5. Study Procedures

6.5.1. Visit 1

After obtaining consent, ensuring the subject meets study inclusion/exclusion criteria, and randomizing the subject, study personnel will photograph the site to be irradiated. Study personnel will collect vital signs. Subjects will complete the Dermatology Life Quality Index. Study personnel will provide KeraStat Cream to subjects randomized to receive KeraStat Cream. Subjects randomized to standard of care will follow the instructions of their radiation oncologist. Study personnel will provide subjects with a daily diary form where subjects will note symptoms or treatment details of concern.

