1. SYNOPSIS

Name of Company:Name of Product:Type of Study:KeraNetics, LLCKeraStat® CreamClinical Proof of Concept

Title of Study: Pilot Study: KeraStat® Cream for Radiation Dermatitis

Investigator(s): [name], PhD; [name], PhD

Study Period: Estimated screening expected to start March 2018; Expected completion September 2018

Phase of Development: Design & Development (Phase 3 of Design Control)

Objective(s):

Primary:

- To assess feasibility (compliance of use)
- Collect data for designing a larger future trial evaluating KeraStat Cream

Secondary:

- To assess the safety and tolerability of KeraStat Cream in subjects at risk of radiation dermatitis
- To assess the effectiveness of KeraStat Cream compared to standard of care to manage the symptoms of radiation dermatitis in subjects being treated with radiation therapy
- To estimate amount of KeraStat Cream used per patient and coverage on skin

Methodology: This is a randomized, open label study.

Number of Subjects:

Sufficient subjects will be screened and enrolled such that 24 total subjects, 12 subjects per treatment group, will complete the study through the Follow-Up Visit. With 12 participants in each treatment group, we will be able to calculate a 95% confidence interval around the compliance rate in each group with a maximum margin of error of 0.283. Comparisons between groups for effectiveness will have 80 percent power to detect a difference of 1.2 standard deviations. Results of the current study are intended to provide descriptive endpoint data to inform the design of a future clinical evaluation of product effectiveness.

Study Overview:

Study Periods:

The length of study participation for a subject is about 8-12 weeks, depending on the length of radiation treatment. The study will extend 4-6 weeks beyond the end of radiation therapy. The study will begin with a Screening Visit during treatment planning followed by weekly assessments during radiation therapy, and a follow up visit 4-6 weeks after completion of therapy. There is a total of 5-7 visits.

Study Assessments:

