At the Screening/Baseline Visit (Visit 1, Week 0), following informed consent, initial eligibility will be verified per the inclusion/exclusion criteria and demographics and brief medical history will be collected. Subjects will be randomized to receive standard of care or KeraStat Cream. A physical exam and photograph of the area to be irradiated will be obtained, and subjects will complete the Dermatology Life Quality Index.

During the course of radiation therapy (4-6 weeks) and for the duration of the post RT treatment period (4-week follow up), subjects will complete a daily diary detailing symptoms and treatment details. Weekly from week 2 of RT until the end of treatment, study staff will assess the subject for radiation dermatitis by recording the RTOG for Radiation-Induced Acute Skin Toxicity scores and taking photographs. The same evaluation will be performed at the follow up visit after treatment. Subjects will complete the Dermatology Life Quality Index at each visit.

Inclusion Criteria:

Subjects must meet all of the following criteria:

- 1. Age ≥ 18
- 2. Female
- 3. Diagnosis of early stage (stage 0-2) breast cancer and scheduled to receive 4-6 weeks of fractionated radiation therapy as part of breast conserving therapy following lumpectomy

Exclusion Criteria:

Version: 00 03-01-2018

Effective Date:

Name of Company:Name of Product:Type of Study:KeraNetics, LLCKeraStat® CreamClinical Proof of Concept

To participate in the study, subjects must not meet any of the following criteria:

- 1. Previous radiation therapy to the area to be treated with radiation therapy
- 2. Receiving palliative radiation therapy
- 3. Low dose radiation protocol
- 4. Unhealed or infected surgical sites in the irradiation area
- 5. Patients undergoing cytotoxic chemotherapy or concurrent Herceptin as part of overall treatment plan (tamoxifen/aromatase inhibitor allowed)
- 6. Use of oral corticosteroids or topical corticosteroids in the irradiation area
- 7. Subjects with an autoimmune disease affecting the skin (e.g., scleroderma, systemic lupus erythematosus, psoriasis) are excluded. A history of other autoimmune disease that does not have direct skin involvement (e.g. rheumatoid arthritis, inflammatory bowel disease, multiple sclerosis) does not exclude participation on the study unless the subject requires active treatment with systemic steroids, immune suppression or biologic agents, or systemic chemotherapeutic agents (methotrexate or cyclophosphamide).

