- 8. Skin disease in target irradiation area
- 9. Known allergy to the standard of care or any of the ingredients in KeraStat Cream

Test Product(s), Dose, and Mode of Administration:

Investigational: KeraStat® Cream should be applied topically to the irradiation area and 1cm beyond the border of the affected area twice daily. Expel the cream from the tube. Smooth the cream over the target area to cover with a thin layer; do not rub the cream in.

Control: The standard skin care product should be applied topically to the irradiation area and 1cm beyond the border of the affected area twice daily. Smooth the product over the target area to cover with a thin layer; do not rub the product in.

Duration of Treatment:

The length of study participation for a subject is about 8-12 weeks.

Concomitant Medication Restrictions:

Chemotherapy, steroids

Criteria for Evaluation:

Effectiveness Evaluation:

Primary

- Safety and tolerability will be evaluated throughout the study utilizing patient reported outcomes
- Adverse events will be recorded throughout the study.

Secondary

- Maximum severity of radiation dermatitis as assessed by the RTOG Criteria for Radiation-Induced Acute Skin Toxicity.
- Number of subjects with Grade I radiation dermatitis
- Number of subjects with Grade II radiation dermatitis
- Number of subjects with moist desquamation present
- Change from baseline in the Dermatology Life Quality Index

Statistical Methods:

Feasibility:

Feasibility will be determined based on the average number of applications per week for a participant. Participants who average at least 10 applications per week will be classified as compliant. A 95% confidence interval will be calculated for the observed compliance rate. Along with the compliance rate, the number of tubes of KeraStat Cream used and the estimated surface area (bra size used as a surrogate) to be covered for each participant will be used to evaluate the coverage.

Safety:

Version: 00 03-01-2018

Effective Date:

Name of Company:Name of Product:Type of Study:KeraNetics, LLCKeraStat® CreamClinical Proof of Concept

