11.3. Quality of Life

Subject quality of life will be measured using the Dermatology Life Quality Index. Subjects will complete the index at each visit. Quality of care will also be assessed qualitatively through examination of daily diary notes.

Version: 00

Effective Date:

03-01-2018

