12. STATISTICS

12.1. Description of Statistical Methods

Descriptive statistics will calculated and used to inform additional device development and to inform a power calculation for a follow on study, if required. The completion rate will be used as a measure of feasibility, with participants with an average of 10 or more applications per week being classified as compliant. A 95% confidence interval will be calculated around the estimate of compliance. After summary statistics are calculated by group, a t-test will be used to compare the two treatment groups for the effectiveness outcomes of DLQI score and RTOG score. A Fisher's exact test will be used to compare skin appearance issues between the groups. The counts for each type of adverse event will be summarized by grade and treatment group. For the KeraStat treatment group, the mean coverage will be calculated per square centimeter.

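### Visit 1 lists randomization before the baseline DLQI in an open-label study, so the baseline for the change-from-baseline endpoint may be recorded with the arm already known

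*Combined protocol and SAP*

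**What the plan says.** Section 6.5.1 describes Visit 1: "After obtaining consent, ensuring the subject meets study inclusion/exclusion criteria, and randomizing the subject, study personnel will photograph the site to be irradiated". It then lists vital signs, and after them: "Subjects will complete the Dermatology Life Quality Index. Study personnel will provide KeraStat Cream to subjects randomized to receive KeraStat Cream". The synopsis (Study Assessments) likewise mentions randomization first and continues: "A physical exam and photograph of the area to be irradiated will be obtained, and subjects will complete the Dermatology Life Quality Index".

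On blinding, the synopsis states: "This is a randomized, open label study". Its secondary effectiveness criteria include "Change from baseline in the Dermatology Life Quality Index".

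Section 6.1 says of timing: "Once the patient has consented to participate in the study, their baseline pre-RT assessments can be completed during the radiation treatment-planning process". Table 2 in that section puts Screening and Baseline at the same Visit 1, Day 1, with no window. Sections 6.4 and 8.3 say that subjects are randomized, but not how, nor when the subject is told her arm.

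For the analysis, section 12.1 states that "a t-test will be used to compare the two treatment groups for the effectiveness outcomes of DLQI score and RTOG score", without saying whether the score is a change or a follow-up value. No baseline adjustment is mentioned. Section 11.3 adds: "Subjects will complete the index at each visit".

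**The concern.** A baseline value should be one that the assignment cannot have influenced. The DLQI is completed by the subject. If she already knows whether she will receive the new cream or physician-directed care, that knowledge may colour her answers, for example through disappointment or expectation. A site that follows the written order may collect the baseline under exactly that condition.

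At stake is the secondary endpoint of change from baseline in DLQI. A difference between arms that exists only because of how the baseline was answered would appear, with its sign reversed, as a difference in change. Pilot status does not remove the issue. One primary objective is to collect data for a larger trial, and section 12.1 uses the descriptive statistics for that trial's power calculation. The Visit 1 procedure could also be carried forward.

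**Working it through.** **1. Order of events, side by side**

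| Source | Order given |
|---|---|
| Section 6.5.1 | consent, eligibility, randomization → photograph → vital signs → DLQI → cream dispensed → diary |
| Synopsis, Study Assessments | consent, eligibility, demographics and history → randomization → physical exam, photograph and DLQI |
| Section 6.1 | baseline assessments any time after consent, during treatment planning; no order relative to randomization |
| Table 2 | Screening and Baseline both Visit 1, Day 1 |
| Sections 6.4 and 8.3 | subjects are randomized; disclosure not addressed |

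Both descriptions of Visit 1 put randomization first, and no section gives the opposite order. There is no separate earlier baseline visit. Only section 6.5.1 uses explicit sequence wording, and there it governs the photograph; the DLQI follows in list order. On that order the DLQI still precedes dispensing, so the issue is knowledge of the arm, not exposure to the product.

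**2. The plan's own figure**

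Section 12.2 gives 80% power for a 1.2 SD difference with 12 per group. A two-sample t-test (noncentral t) with an assumed two-sided alpha of 0.05 gives 80.2%, so the figure reproduces. Reordering Visit 1 changes none of its inputs.

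**3. How a reporting shift enters each analysis**

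Let dB be the between-arm shift in DLQI due to knowing the arm at baseline, dF the same at follow-up, and b the within-arm slope of follow-up on baseline. The bias in the treatment contrast is:

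- change from baseline: dF − dB
- baseline-adjusted: dF − b·dB
- unadjusted follow-up: dF

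With b = 0.3, 0.5 and 0.7 (assumed):

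| Scenario | Change | Adjusted | Follow-up only |
|---|---|---|---|
| Shift at baseline only (dB = 1, dF = 0) | −1.0 | −0.3 / −0.5 / −0.7 | 0.0 |
| Same shift at both times (dB = dF = 1) | 0.0 | 0.7 / 0.5 / 0.3 | 1.0 |
| Baseline taken before assignment (dB = 0, dF = 1) | 1.0 | 1.0 | 1.0 |

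A simulation with 12 per arm, equal SDs and 20,000 runs per scenario gave the same values.

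**4. Illustration of scale, on assumed inputs**

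Suppose there is no true effect and one arm's baseline alone shifts by s SD. With baseline–follow-up correlation r, the SD of change is √(2(1 − r)), and the standardized bias is s / √(2(1 − r)).

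- s = 0.2: r = 0.3 gives 0.2/1.183 = 0.169 and 6.8% rejections; r = 0.7 gives 0.2/0.775 = 0.258 and 9.3%.
- s = 0.5: r = 0.3 gives 0.423 and 16.8%; r = 0.7 gives 0.645 and 32.7%.

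The nominal rate is 5%. Neither s nor r is in the documents, and a baseline-only shift is the scenario least favourable to the current order. These figures show what could happen; they do not estimate what will.

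**The case against.** Four arguments deserve weight.

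- **The sequence is weakly stated.** The explicit wording covers only the photograph, and section 6.1 would let a site complete the DLQI before randomizing. The time of disclosure is unknown. This is right, and it is why the conclusion is that the baseline can be post-assignment, not that it will be. Still, no section requires the safer order, and the two that describe the visit suggest the other one.
- **The planned test may be unaffected.** The synopsis statistical methods and sections 12.1 and 12.2 all refer to the DLQI score; only the endpoint list names change. If follow-up scores are compared without adjustment, a baseline shift has no effect. This stands as a limit. The listed change endpoint is exposed all the same.
- **The fix can leave more bias in the change score.** If the same shift persists, it cancels under the current order (0.0) and remains under the proposed one (1.0). More generally, for positive dF the current order has the smaller change-score bias whenever dB lies between 0 and 2·dF, since then |dF − dB| < |dF|. The algebra is correct, and the documents cannot show which case applies. But relying on two unknown shifts to offset each other is no reason to keep a baseline that assignment can influence. With a pre-assignment baseline, what remains is the ordinary open-label reporting bias at follow-up.
- **The consequence is small.** The DLQI change is one of five secondary criteria in a pilot meant to be descriptive. Skin disease and unhealed or infected surgical sites in the field are excluded, which may keep baseline scores low, although no baseline data are given. This limits the weight of the point but does not remove it.

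**Conclusion.** The concern holds, with modest weight. As written, the Visit 1 procedure allows the self-reported DLQI baseline to be recorded after assignment in an open-label study, and nothing in the protocol prevents it.

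The size of any resulting bias is unknown. The share of a baseline-only shift that reaches the result is 100% for change from baseline, b × 100% with baseline adjustment, and 0% for unadjusted follow-up scores. The exposure depends on three things the documents leave open: whether the subject knows her arm when she answers, whether that knowledge changes her answers differently at baseline and at follow-up, and which form of the DLQI is analysed. It is limited to one secondary endpoint.

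**What to change.** Reword section 6.5.1 and the Study Assessments paragraph of the synopsis so that the order is: consent; eligibility; DLQI (and, for convenience, vital signs, physical exam and photograph); then generation or disclosure of the assignment; then dispensing of product and diary. State explicitly that the baseline DLQI is completed before the subject learns her arm.

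The cost is wording only. Visit, staff and procedures stay the same, section 6.1 already permits assessments once consent is given, and sample size and power are unchanged. The change protects the baseline only: DLQIs at later visits will still be answered with the arm known, and that should be acknowledged as a limitation when the DLQI results are interpreted.

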6.5.2. Weekly Visits through Radiation Therapy

During regular visits with medical staff, study subjects will also meet with study staff. Study staff will obtain photographs of the area of irradiation and collect the daily dairy forms. Study personnel will collect vital signs and the physician's assessment of the presence and quality of radiation dermatitis using the RTOG scale as well as the physician's assessment of skin dryness, appearance of inflammation, and the skin's natural barrier. Any adverse events will be noted and addressed. Subjects will complete the Dermatology Life Quality Index. Study personnel will provide KeraStat Cream, as needed, to subjects randomized to receive KeraStat Cream. Subjects randomized to standard of care will follow the instructions of their radiation oncologist. Study personnel will provide subjects with a daily diary form where subjects will note symptoms or treatment details of concern.

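### Visit 1 records no RTOG, dryness, inflammation or barrier score, so skin change left by surgery cannot be formally separated from radiation-induced change at the early visits

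*Combined protocol and SAP*

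**What the plan says.** Section 6.5.1 sets out Visit 1. After consent, the eligibility check and randomization, "study personnel will photograph the site to be irradiated. Study personnel will collect vital signs. Subjects will complete the Dermatology Life Quality Index". The cream is handed out at the same visit to those allocated to it. The Synopsis adds an examination: "A physical exam and photograph of the area to be irradiated will be obtained, and subjects will complete the Dermatology Life Quality Index". Neither place asks for a graded skin score. Section 6.1 mentions pre-RT baseline assessments but does not itemise them.

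The graded items appear in Section 6.5.2 (weekly visits) and Section 6.5.3 (close-out): the RTOG scale and the "physician's assessment of skin dryness, appearance of inflammation, and the skin's natural barrier". The Synopsis gives the timing: "Weekly from week 2 of RT until the end of treatment, study staff will assess the subject for radiation dermatitis". Table 2 puts the first evaluation, Visit 2, at RT Day 8 ±2 days.

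On the state of the skin, Section 6.1 says that "RT will begin 4 to 10 weeks after surgery". Section 7.2 excludes unhealed or infected surgical sites and skin disease in the field.

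On analysis, the Synopsis lists maximum RTOG severity and counts of Grade I, Grade II and moist desquamation. DLQI is the only endpoint defined as change from baseline. Section 11.5 estimates, at each time point, the proportion of women with radiation-induced EASR and its 95% confidence interval, and the incidence for any grade and for grade 2 and higher. Section 12.1 compares RTOG scores by t-test and adds: "A Fisher's exact test will be used to compare skin appearance issues between the groups". It states no baseline adjustment and does not define an issue as new or worsened.

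**The concern.** Section 11.5 wants the proportion of reactions that radiation caused, and Section 12.1 wants a comparison of skin-appearance issues. Both need to know what the skin looked like before radiation and before product. Table 2 names Visit 1 the baseline visit, yet the physician-scored outcomes have no baseline value.

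The exclusions leave room for healed skin that is still red, swollen or dry. Such a finding, if recorded at RT Day 8, has no earlier score to be set against. One of the two primary objectives is to collect data for designing a larger trial, so an inflated early event rate would carry into that design. A baseline not taken before radiation starts cannot be recovered.

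**Working it through.** **Plan's own figures.** The plan gives no figure on this point. Its sample-size figures in Section 12.2 reproduce and are not in dispute. The maximum margin is 1.96 × √(0.25/12) = 0.283. A two-sample t-test with 12 per group, a difference of 1.2 SD and two-sided alpha 0.05 (assumed, since the plan does not state alpha) has power 0.802.

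**Inputs.** From the documents: 24 subjects, 12 per arm (Section 12.2), and about 85% of RT patients having a moderate-to-severe skin reaction (Section 4.1). Assumed: K, the number of the 24 with residual redness, swelling or dryness at entry. The documents give no rate, so a range is shown.

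**Chance imbalance between arms.** With K affected subjects divided at random into two arms of 12, the probability that i fall in one arm is C(12,i) × C(12,K−i) / C(24,K). Summing over splits in which the arms differ by 3 or more:

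| K | Splits that count | Calculation | Probability |
|---|---|---|---|
| 1, 2 | none possible | – | 0 |
| 3 | 3:0 | 2×220/2,024 | 0.22 |
| 4 | 4:0 | 2×495/10,626 | 0.09 |
| 5 | 5:0, 4:1 | 2×(792+5,940)/42,504 | 0.32 |
| 6 | 6:0, 5:1 | 2×(924+9,504)/134,596 | 0.16 |
| 7 | 7:0, 6:1, 5:2 | 2×(792+11,088+52,272)/346,104 | 0.37 |

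The figures zigzag because the gap always has the same parity as K: for even K, a gap of 3 or more means 4 or more. Quoting only odd K would overstate the risk.

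**From a finding to an event rate.** A residual finding changes a rate only if the assessor scores it and the subject would otherwise have had no event. Let p be the probability that she would have had the event anyway. Her expected effect on her arm's rate is then at most (1/12) × (1−p):

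- p = 0: 8.33 percentage points
- p = 0.5 (assumed): 4.17 points
- p = 0.85 (the Section 4.1 figure, used for any-grade maximum severity): 8.33 × 0.15 = 1.25 points

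A gap of 3 subjects is therefore at most 3 × 8.33 = 25 points, and about 3 × 1.25 = 3.75 points at p = 0.85.

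For the proportion over all 24 subjects, the excess is at most (K/24) × (1−p). For K = 1 to 7 this is 4.2 to 29.2 points at p = 0, and 0.6 to 4.4 points at p = 0.85. The documents give no p for RT Day 8. It should be lower early in treatment than for the maximum over the whole course, so the early visits are the most exposed.

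**The case against.** The case on the other side has force, and much of it stands.

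- **Attribution.** Section 6.5.2 asks for the physician's view of radiation dermatitis, not of all redness, and Section 11.5 counts radiation-induced reactions. The assessor has a pre-RT photograph and, under the Synopsis, an examination. The Synopsis also plans to examine changes in physical examination results from screening onward. A reader might infer that surgical change will be counted as radiation effect. The documents support only that it may be. Still, neither the photograph nor the examination is graded on the four items, no section plans to grade the photographs, and Section 6.5.1 omits the examination.
- **Product effect.** A reader might infer that the gap biases the comparison of cream with standard care. It does not: allocation is randomized, so residual change is balanced in expectation. Imbalance at 12 per arm is sampling error that Fisher's test already allows for.
- **Grade.** Section 4.2 classes grade 2 or 3 as EASR. Mild residual redness or dryness would not meet that, so applying an inflation to the roughly 30% Grade 2-or-worse rate would need every residual finding to be scored at that grade. The documents give no ground for this.
- **Maximum severity.** Where the later radiation reaction equals or exceeds the residual finding, the maximum grade is unchanged.
- **Timing.** Section 6.1 dates the start of RT, not Visit 1, at 4 to 10 weeks after surgery. Visit 1 falls earlier, during planning, so its score would describe the skin somewhat before the first fraction.

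What survives is narrower: no structured score exists before radiation and product, and the analysis has no rule for pre-existing findings.

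**Conclusion.** The point holds as a gap in baseline measurement. RTOG, dryness, inflammation and barrier are first scored after about a week of RT and after dispensing, so residual post-surgical change in healed skin cannot be formally separated from radiation-induced change. The exposed results are the early-visit any-grade proportions in Section 11.5, the Grade I count and the skin-appearance items in Section 12.1. Grade 2-or-worse counts, moist desquamation and most maximum-severity results are little affected. Compliance is untouched, and DLQI has its own baseline.

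The size cannot be fixed from the documents. It rests on the assumed K, on whether the assessor scores residual change as dermatitis, and on how many affected subjects would react anyway. The event-rate figures above are upper limits given K and p. This is a worthwhile, inexpensive improvement and not a threat to the validity of the randomized comparison.

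**What to change.** In Section 6.5.1, before randomization and in both arms, record the same physician RTOG, dryness, inflammation and barrier scores as in Section 6.5.2. List there the physical examination that the Synopsis already plans. In Section 12.1, tabulate these baseline scores by arm. Keep maximum RTOG severity as an absolute grade, and additionally report the skin-appearance items and per-visit any-grade dermatitis as new or worse than Visit 1.

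The cost is a few minutes at an existing visit, some extra CRF fields and the matching protocol wording. It needs no new visit and no change to the sample size.
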